8.2 Serious Adverse Events (SAEs)

A Serious Adverse Event (SAE) is defined as an event which:

- is fatal or life-threatening
- results in persistent or significant disability/incapacity
- constitutes a congenital anomaly/birth defect
- requires inpatient hospitalization or prolongation of existing hospitalization, unless hospitalization is for:
 - routine treatment or monitoring of the studied indication, not associated with any deterioration in condition.
 - elective or pre-planned treatment for a pre-existing condition that is unrelated to the indication under study and has not worsened since the start of study drug.
 - treatment on an emergency outpatient basis for an event not fulfilling any of the definitions of a SAE given above and not resulting in hospital admission.
 - social reasons and respite care in the absence of any deterioration in the patient's general condition.
- is medically significant, i.e., defined as an event that jeopardizes the patient or may require medical or surgical intervention to prevent one of the outcomes listed above

The number and proportion of participants who experience SAEs will be analysed and presented. The appropriate grading of severity of the SAEs will also be presented in counts and proportion. A listing of SAEs experienced will be included per participant.

If any serious adverse events occur in >5% of individuals who receive either intervention, the time to occurrence of the adverse event will be summarized using median (IQR) and graphically with Kaplan-Meier curves.

Table shell 6. Serious adverse events – summary

SAE	LDA, n(%)	Placebo, n(%)	Overall
Total			
Listed			

Table shell 7. Serious adverse events – list

record_id	SAE	Relationship	Comments including action taken

8.3 Prior and Concurrent Medications

The proportion of participants who have used aspirin in the preceding month will be estimated.

9 Sub-group Analyses

The efficacy analyses of LDA on occurrence of the composite outcome (at least one of IUGR, miscarriage, and perinatal death) will be repeated in the following subgroups:

- a) Concurrent medications – hydroxyurea
- b) Hemoglobin genotype – Hb SS vs. Hb SC
- c) Body mass index at ANC enrolment

Subgroup analyses will only be considered if the minimum number of participants in each subgroup is at least 30 people.

10 Reporting Conventions

P-values ≥ 0.001 will be reported to 3 decimal places; p-values less than 0.001 will be reported as “ <0.001 ”. The mean, standard deviation, and any other statistics other than quantiles, will be reported to one decimal place greater than the original data. Quantiles, such as median, or minimum and maximum will use the same number of decimal places as the original data. Estimated parameters, not on the same scale as raw observations (e.g. regression coefficients) will be reported to 3 significant figures.

11 Quality Assurance of Statistical Programming

A second review statistician will independently check the code and output for the entire analyses. To ensure fidelity of results, another statistician will review the analysis based on the codes supplied and by using another statistical software. Stata version 18 (StataCorp, USA) and R-Studio statistical software will be the main statistical software for the analyses. High quality code that is understandable, and reproducible will be produced. Generous annotation and explanations of steps will be performed. Data specifications such as the population of analysis, date and time included, and the description of desired output from analysis will be included.

12 Summary of Changes to the Protocol and/or SAP

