5.5 Multiple Testing

There is one primary endpoint in our analysis, and no adjustment for multiple testing will be done(26). Thus, our analysis's alpha level for statistical inference will be 0.05, and all p-values will be presented to the third decimal place.

6 Summary of Study Data

Baseline covariates will be summarized and stratified by intervention arm to describe the population . Continuous variables will be summarized using the following descriptive statistics, n (non-missing sample size), mean, standard deviation (SD), medians, interquartile ranges (IQR), minimum and maximum. The frequency and percentages (based on the non-missing sample size) of observed levels will be reported for all categorical measures. In general, all summary tables will be structured with a column for the overall population. Summary tables will also be presented for each treatment and will be annotated with the total population size relevant to that table/treatment. The number of missing observations will be presented in the footnote of each table.

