7.1 Primary Efficacy Analysis – a composite of IUGR, perinatal death or miscarriage

The main analysis will be conducted in the ITT population. The frequency of the primary endpoint will be presented as N and percent of the total study population and by treatment group (LDA vs. placebo). The frequency of the components of the composite endpoint will also be considered.

Log-binomial regression models will be used to evaluate the effect of LDA (vs. placebo) on the occurrence of the composite endpoint, and risk ratios and confidence intervals will be presented. All components of the composite endpoint are included as secondary endpoints, and their analysis is described in 7.2 below. In some cases, the log-binomial models may not converge, and log-Poisson models, which provide consistent but not fully efficient estimates of the relative risk, and its confidence intervals will be used(27).

Baseline covariates that are strongly prognostic of the outcome or imbalanced in the treatment arms may be included in the model if their inclusion improves the precision of the estimates(28,29). Baseline covariates identified from previous studies to be strongly prognostic of the outcome or its components include: maternal age(30–32), hemoglobin genotype(8,33), parity(31), body weight (34–36), educational attainment(37), marital status(35), preeclampsia(31,35), and hemoglobin(38). It is important to note that much of this evidence is from studies in the general population rather than among people with sickle cell disease – and this may impact the extent to which these factors may be prognostic in this study population. The estimates will be regarded as improved if the distance between the upper and lower confidence limits reduces by >10%.

Cluster-robust standard errors from the sandwich package will be employed, clustered on sites.

Table shell 2: Primary composite outcome and components

Outcome	Level	LDA, n(%)	Placebo, n(%)	Risk ratio	Confidence intervals	P-value
IUGR, perinatal death or miscarriage	At least one					
	None					
IUGR	Yes					
	No					
Miscarriage	Yes					

Outcome	Level	LDA, n(%)	Placebo, n(%)	Risk ratio	Confidence intervals	P-value
	No					
Perinatal death	Yes					
	No					

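### SAP section 9 repeats the composite analysis inside each subgroup and plans no interaction test, so it has no valid way to say whether the aspirin effect differs between HbSS and HbSC

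*SAP*

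**What the plan says.** SAP section 9 states that the analysis of the composite (growth restriction, miscarriage or perinatal death) "will be repeated in the following subgroups". The factors are "Concurrent medications – hydroxyurea", "Hemoglobin genotype – Hb SS vs. Hb SC", and body mass index at antenatal enrolment. One condition is attached: "Subgroup analyses will only be considered if the minimum number of participants in each subgroup is at least 30 people".

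The analysis to be repeated is in SAP section 7.1: "Log-binomial regression models will be used to evaluate the effect of LDA (vs. placebo) on the occurrence of the composite endpoint". Its table shell has columns for the risk ratio, confidence interval and p-value. SAP section 5.5 states that "our analysis's alpha level for statistical inference will be 0.05" and that "no adjustment for multiple testing will be done".

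Neither document mentions a treatment-by-subgroup term, a heterogeneity test or a ratio of risk ratios, and nothing marks the subgroup results as exploratory. The analysis plan in Protocol section 9.3 contains no subgroup analysis, so it does not fill the gap.

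**The concern.** Two p-values from two subgroups each answer whether aspirin works in that subgroup. Neither answers whether the effect differs between them. With low power in each part, one result can fall below 0.05 and the other above it although the true effect is the same.

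This matters for how the trial will be used. Protocol section 1.2 hopes for a recommendation covering pregnant women with sickle cell disease, and section 15.0 says the findings will be used in counselling. A chance contrast between genotypes could steer advice away from one of them.

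Membership of two of the three factors is also open. Hydroxyurea use is recorded on the enrolment form (Protocol Appendix 06) and again on each follow-up form (Appendix 07), and the SAP does not say which record defines the subgroup. BMI has no cut-offs in section 9 or SAP Table 3.

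**Working it through.** **Inputs from the documents.** Control rate 20% and a 50% relative reduction, so 20% against 10%, with 198 evaluable per group (SAP section 4). The hypothesis of a 50% lower composite incidence has no difference by genotype (SAP section 2.2). Allocation is 1:1 and alpha 0.05, taken here as two-sided.

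**Assumptions.** The genotype split is not stated; 50:50, 75:25 and 90:10 are shown. The 20% is the growth-restriction rate. The composite rate is not given and cannot be lower than the rate of its component, so 30% and 40% are also shown. Clustering by site is ignored.

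**The plan's own figure.** With n per arm, d = p1 − p2 and p̄ the mean of p1 and p2, power = Φ[(d − 1.96·√(2p̄(1−p̄)/n)) / √((p1(1−p1)+p2(1−p2))/n)]. At n = 198 and 20% against 10% this is 79.8%; 90% power needs 266 per arm. The stated 90% therefore does not reproduce for a two-sided test. That is a separate matter, but it means subgroup power starts from a lower base.

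**Power within subgroups at 20% against 10%.**
- n = 99: (0.1 − 1.96 × 0.0508)/0.0503 ≈ 0.01, power 50%.
- n = 148.5: (0.1 − 1.96 × 0.0414)/0.0410 ≈ 0.46, power 68%.
- n = 49.5: (0.1 − 1.96 × 0.0718)/0.0711 ≈ −0.57, power 28%.
- n = 15 (half of the 30-woman minimum): power 11%.

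**Chance of one significant and one not, under an identical risk ratio of 0.50.** The two genotype groups are independent, so with powers A and B it is A(1−B) + B(1−A). At 75:25 and a 20% control rate: 0.676 × 0.717 + 0.283 × 0.324 = 0.485 + 0.092 = 0.576.

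| Control rate | 50:50 | 75:25 | 90:10 |
|---|---|---|---|
| 20% | 50% | 58% | 69% (0.685) |
| 30% | 41% | 55% | 76% |
| 40% | 22% | 42% | 72% |

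With no effect in either genotype the nominal figure is 2 × 0.05 × 0.95 = 9.5%; simulation with a Wald test on the log risk ratio gives about 5% to 9%.

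**Several null subgroup tests.** With BMI in two groups (assumed) there are six tests. If they were independent, the chance of at least one p<0.05 would be 1 − 0.95⁶ = 26%. The three factors divide the same women, so the tests are correlated; simulation with 396 women and a 20% event rate gives about 21%.

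**What an interaction test would do.** When the risk ratios are identical, it wrongly declares a difference in about 2% to 5% of simulated trials. Its power is low. The variance of the log ratio of risk ratios is the sum, over the four genotype-by-arm cells, of (1−p)/(np). At 50:50 this is 2 × (0.8/19.8 + 0.9/9.9) = 0.263, so the standard error is 0.512. The ratio detectable with 80% power is exp(2.80 × 0.512) ≈ 4.2. At 90:10 it is about 10.9.

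**The case against.** Several limits are fair.

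- **No verdict rule.** A reader might infer that the SAP will judge subgroups by significance. It does not say so. It makes no subgroup claim, has no subgroup table shell and names one primary endpoint. The defect is an omission, although the repeated analysis carries a p-value and no other comparison is provided.
- **Conflicting results are not likely in every case.** A high chance of discordance needs a real common benefit, and it depends on a genotype split and a composite rate that the documents do not give. At a 40% control rate and equal groups it is about 22%.
- **Not an effect of unequal size alone.** At 50:50 the groups are equal and discordance is still 50% at the 20% rate, from low power and chance. Nor do all discordant results favour the larger group: at 75:25 about 48% of trials show only the larger group significant and 9% only the smaller. The documents do not say which genotype will be more numerous.
- **Hydroxyurea.** A reader might infer that this subgroup is planned on use after randomisation. The documents do not support that; the timing is simply not stated.
- **A weak remedy.** The interaction test will rarely be significant. That is a reason to report an interval and to caution the reader, not to leave the comparison untested.

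The primary result is unaffected by any of this. What stands is that section 9 names a method that cannot answer whether the effect differs.

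**Conclusion.** The point holds as an omission in a secondary analysis that should be corrected. Section 9 offers no test of whether the effect differs between subgroups.

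At the plan's own 20% rate and a shared risk ratio of 0.50, separate testing would give conflicting genotype results in half or more of trials at each split shown. Over control rates of 20% to 40% the range is 22% to 76%. These figures rest on 198 evaluable per group, a two-sided 5% test, assumed genotype splits and no allowance for clustering by site. The hydroxyurea and BMI definitions are unsettled rather than wrong, and can be settled while the data are still blinded.

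**What to change.** Amend SAP section 9 as follows.

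1. For each factor, fit one log-binomial model (log-Poisson if it does not converge) with treatment, subgroup and their interaction.
2. Report the subgroup risk ratios with confidence intervals, the ratio of risk ratios with its interval, and the interaction p-value. Drop the within-subgroup p-values.
3. Label the analysis exploratory. State that the interaction test has low power (80% power needs a ratio of risk ratios of about 4 or more), so a non-significant result does not show equal effects.
4. Define the hydroxyurea subgroup from the enrolment e-CRF.
5. Fix the BMI cut-offs before unblinding.

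The cost is SAP wording and one added model term per factor. The data, software and sample size do not change.

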12.1 Adjustments of Statistical Analysis Plan from Protocol

The SAP in the protocol has been revised extensively in this current SAP. Major highlights of the revision include:

- i. This SAP provides more detail on the statistical analysis approach than provided for in the protocol.
- ii. The preferred binomial model for the primary outcome in the protocol was the logistic regression. We now opt for the log-binomial model as this yields risk ratios which are easier to interpret than the odds ratios from logistic regression(40).
- iii. The protocol specified that analysis would be by multivariate regression.
 - a. Multivariate regression is a valid approach for analysing clinical trials with multiple outcomes, as it accounts for any correlation between the outcomes(41,42). We however opt to analyse the multiple components of the composite outcome as a single outcome – this approach is simpler, easier to understand, and could increase the number of events in our study.
 - b. The term “multivariate” is often wrongly used interchangeably with “multivariable”(43). We now remove the term “multivariate”, and instead explain our approach to selecting covariates that we may adjust for in our model.

